3.9 Clinical safety assessment

1) Adverse events

Definition of the adverse events

Adverse event (or adverse experience, AE): any adverse medical event occurring in a subject or clinical subject, not necessarily causally related to treatment.

The AE can therefore be any bad or non-intended signs (e. g., including abnormal laboratory results), symptoms, or transient drug-related disease, which should be considered for medication involvement.

Adverse events occurring both before and after treatment were considered as adverse events according on management needs. Therefore, safety monitoring (reporting adverse events or serious adverse events) should be performed from subject enrollment to the end of

the study. Therefore, adverse events occurring during signing the informed consent and initiation of study treatment were also considered as AEs.

Adverse drug reactions (ADRs): All toxicities and non-intended reactions to the drug related to any dose should be considered as adverse drug reactions (ADRs).

Response to the drug means that there is at least a reasonable possibility of a causal relationship between the drug and the AE, meaning that this relationship cannot be excluded.

Serious Adverse Event (SAE): means all adverse medical events occurring at any drug dose:

- Lead to death
- life-threatening

Note: "serious" and "life threatening" are defined as an adverse event when the subject has the adverse event; rather than an adverse event that the more serious may lead to death.

- Patients require hospitalization or extension of existing hospitalization
- Leading in persistent or significant incapacity / disability
- Congenital malformations or birth defects

Important medical events: important medical events, do medical and scientific appraisal to decide whether to report is appropriate, these important medical events may not immediately life threat or cause death or hospitalization, but may harm subjects or may need interference to prevent the occurrence of the other results, usually should also be considered serious. For example, some adverse events require severe treatment in the emergency room, or management of allergic bronchial asthma at home; malignant fluid or convulsions without hospitalization; drug dependence and abuse, or malignant tumors histologically different from the primary tumor.

Other events that should be addressed as SAEs: Drug exposure during pregnancy / lactation: In principle, pregnancy and lactation are under the exclusion criteria. If a pregnancy occurs during the study, the patient should immediately withdraw from the study and inform the investigator immediately and follow up the patient throughout the pregnancy and postpartum. Even if the mother and child are completely normal without any adverse events, the consequences should be recorded. Even if the pregnancy is not a SAE, use the SAE report form.

Events that should be handled as SAEs: disease progression.

2) Record and evaluation methods of adverse events

All AEs should be recorded in the appropriate part of the Medical Record Report Form (CRF). SAE report forms (including initiation or follow-up reports) should also be completed.

The following aspects of each event should be recorded in the CRF:

- AEs in medical terms, not as a subject;
- Date of occurrence (start date);
- Octime (start time);
- Recovery date (end date);
- Recovery time (end time).

The grading was assessed by the investigator as defined by NCI-CTC version 5.0.

- Level 1 = mild;
- Level 2 = moderate;
- Level 3 = Heavy;
- Grade 4 = life-threatening or disabling;
- Level 5 = death.

The investigator should assess the causal relationship between the adverse events and the study drug; the decisive factor assessed in the record is the temporal correlation between the AEs and the study drug. The causal relationship between the adverse event and the study drug or study protocol is judged as follows:

- Uncorrelation = no temporal relationship with the study drug (too early, too late or not medication), or a reasonable causal relationship between the AE and another drug, associated disease or environment;
- Impossible = a temporal relationship with study drug, but no reasonable causal relationship between AE and study drug;
- Probably = a reasonable causal relationship between AE and study drug. Lack of withdrawal information (withdrawal information) or unclear;
- It is likely that there is a reasonable causal relationship between AE and study drug. Discontinuation (withdrawal from the drug study) had an effect on the response. No redose to prove;
- Clear / definite = a reasonable causal relationship between AE and study drug. Discontinuation has an effect on response and can occur if readministered when clinically feasible.

Measures taken for this study treatment (none, discontinuation, dose reduction, delayed treatment, slowing of intravenous infusion) and other measures (no, concomitant medication,

need for hospitalization, or prolonged hospitalization, surgery, delayed chemotherapy, discontinuation of chemotherapy, chemotherapy reduction) were defined as follows:

- Recovery with sequelae
- Healing without sequelae
- Not healed, but no treatment is needed
- Not healed and need treatment
- die

Toxicity grade / severity was changed

- Serious: Yes or No;
- If the patient has the same AE several times, each must be recorded and re-evaluated.

3) Reporting procedures for serious adverse events

Any serious or medically significant clinical adverse event or laboratory abnormality occurring during the study obligates the investigator to report every serious adverse event to the ADR by telephone or email within 24 hours.

After the telephone report, the written information should be sent by fax. The report shall provide the information of the reporter and recipient including name, address, telephone and fax number, and indicate that the report is "preliminary" report or "follow-up" report. If necessary, the report form shall be accompanied by the relevant medical record report form.

The investigator shall guarantee to the public ethics committee or competent authority any additional information regarding the death of the subject.

All forms must be dated and signed by the responsible person, or signed by an authorized colleague of the responsible person.

4) Monitoring of the adverse events of the subjects

Any adverse events occurring during the study were monitored and followed up until the end of the study. In addition, the SAEs must be reported through the SAE table.

5) Laboratory index evaluation

All laboratories in the hospital for clinical evaluation should meet the basic principles of Good Laboratory Practice (GLP) and the requirements of their hospital.

6) Clinical safety assessment

Version NCI-CTCAE 5.0 will be used to evaluate the clinical safety of the treatment in the study. The occurrence of adverse events will be assessed at each clinical visit.

3.10 statistical analysis

statistical analysis technique

Using computer (SPSS or R) software package, count data adoption rate, mean and 95% credible interval for measurement data; t-test for measurement data when comparing two groups, chi-square test for count data, Kaplan-Meier and Log Rank methods for survival analysis, and Cox proportional risk model for prognosis analysis. The probability P-value was used at any stage, and the statistical significant difference bound was used at 0.05.

Safety analysis: The toxicity evaluation criteria were evaluated according to the NCI-CTC 5.0 criteria. Specific statistical methods are the same as above.

Type of analysis

Prior to database lock, the following three datasets were identified.

The primary efficacy analysis will be performed in all enrolled populations (the intent-to-treat population or the ITT population) and the per-protocol population (PP). Secondary efficacy analysis and exploratory analysis will be performed in the intention-to-treat population. Non-inferiority analysis will be performed in the per-protocol population.

1. Intention-to-treat population

The intention-to-treat population consists of all patients randomized to any of the two treatment arms. Analysis will be performed according to the treatment groups randomassigned by the patients.

2. Population conforming to the protocol

Patients who have not received any dose of chemotherapy or chemoradiotherapy, or those who have suffered a serious violation of the inclusion or exclusion criteria. Analysis will be performed according to the treatment groups randomassigned by the patients.

3. Safety population

The safety population includes all patients who have received at least one dose of chemotherapy or radiotherapy. The Safety population was used to analyze all safety parameters. Patients were assigned to the treatment group based on the medication they actually received.

4. The data that should be excluded during the analysis

There were no excluded data available.

Medium-term analysis

An interim analysis of the efficacy endpoints is not performed in this study. An independent data security monitoring team will monitor the safety data throughout the study. All safety data descriptive analysis will be performed after study treatment for all patients enrolled in this study. This analysis will be strictly limited to the safety data and will not include any efficacy endpoints.

4. research contents

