Effectiveness evaluation criteria	
Tumor evaluation was performed throughout the study and analyzed using the Solid Tumor Efficacy Evaluation (RECIST) criteria (version 1.1,2009). Radiological imaging (CT, MRI) scans were performed, and the clinical complete response rate (cCR), objective response rate (ORR), and tumor staging rate (mrTRG) were determined and calculated for all patients.

statistical method	
Statistical analysis was performed using SPSS23.0 or SAS software. For the PPS and FAS data, and safety indicators for the SS data. Most of the data presented in this study were descriptive. For continuous data, it is

expressed by mean and standard deviation and percentage of index index.

(1) Baseline demographic data and disease characteristics:

Characteristics of the observed patients were summarized by descriptive statistics, including age, sex, clinical stage, and ECOG scores, etc.

(2) Analysis method of the primary endpoint:

After the completion of the whole neoadjuvant treatment, two doctors in the pathology department jointly evaluated the pathological complete response rate (pCR).

(3) Secondary endpoints analysis method:

A. After the end of the whole neoadjuvant treatment, two doctors from the pathology department jointly evaluated the tumor withdrawal grade (TRG), and the pathological decline rate.

B. The imaging results were evaluated by RECIST 1.1 standard to calculate the objective response rate (ORR) and tumor descent rate (mr TRG);

C. Patient quality of life (QoL) was evaluated using the Chinese version of the Cancer Patient Quality of Life Scale [EORTC QLQ-C30] (V3.0);

D. Safety indicators: The evaluation is based on the SS set, using NCI-CTC AE v5.0 criteria, listing the incidence of adverse events and serious adverse events, their clinical presentation characteristics, severity, occurrence time, duration, treatment method, and prognosis.

E. The rate of tumor descent, the rate of anal preservation, incidence of surgical complications, incidence of adverse events and incidence of serious adverse events were all expressed in percentage.

F. Survival analysis was performed by Kaplan-Meier to estimate the 2-year overall survival (OS) and disease-free survival (DFS);

Flow chart of the clinical trial

Flow-chart description of the clinical trial

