2.2 Secondary purpose

- Objective response rate (ORR);
- Clinical complete response rate (cCR);
- Tumor downstaging rate (mrTRG);
- Downstaging rate of tumor pathology;
- Grade of tumor regression (TRG);
- R0 resection rate;
- Anal rate;
- The rate of surgical complications;
- 2-year disease-free survival rate (2-year DFS);
- 2-year overall survival rate (2-year OS);
- Quality of life (including anal sphincter function, bladder function and sexual function);
- Incidence of adverse reactions and serious adverse reactions.

The safety and tolerability of the study protocol will be evaluated according to the incidence and severity of adverse events and graded according to the NCI CTC AE 5.0 standard.

3. The research plan

This topic is a single-arm, single-center, prospective phase II clinical study.

3.1 Whole-course neoadjuvant therapy regimen:

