4.6 Termination of treatment

- Serious adverse events or serious adverse reactions (SAEs) during the study;
- Delay treatment for more than 4 weeks for any reason (meaning all drugs in the delayed regimen).

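### Disease progression is to be handled as an SAE and nothing removes it from the SAE percentage, so a tumour outcome enters the reported safety rate

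*Combined protocol and SAP*

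**What the plan says.** Section 3.9, part 1, lists the usual seriousness criteria and then adds special cases. For pregnancy the instruction is limited to the form: "Even if the pregnancy is not a SAE, use the SAE report form". The line that follows has no such limit: "Events that should be handled as SAEs: disease progression".

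The analysis is described in the Protocol summary, statistical method, item (3). Point D evaluates safety in the safety set, "listing the incidence of adverse events and serious adverse events". Point E adds that "incidence of adverse events and incidence of serious adverse events were all expressed in percentage". Neither point restricts the count by causality. Section 3.10, on data to be left out of the analysis, says only "There were no excluded data available". Under its interim-analysis heading, the same section confines the descriptive safety analysis to safety data and rules out efficacy endpoints.

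The endpoint itself has a different name. Section 2.2 calls it "Incidence of adverse reactions and serious adverse reactions", as does the list of secondary endpoints in the Protocol summary.

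SAE status is also used elsewhere. Section 4.6 lists "Serious adverse events or serious adverse reactions (SAEs) during the study" under termination of treatment, while section 3.5 sets out its own paths for a patient evaluated as PD.

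**The concern.** Progression is already an efficacy outcome in this protocol: it is the PD category in section 3.5, section 4.7 part 1 and the RECIST attachment. Section 4.7 defines PD as growth of more than 20% or a new lesion. Such a finding need not meet any seriousness criterion in section 3.9, so some progressions would be SAEs only because of this one line.

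The resulting SAE percentage would mix failure to control the tumour with harm occurring on treatment. A single-arm trial has no control group in which the same mixing would show. A reader could not tell from the percentage how much of it is progression. What is at stake is one reported secondary endpoint; the primary endpoint, pCR, is not touched.

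**Working it through.** **1. Denominator.** The plan's only relevant figure is N = 35 (section 4.1: 15% versus 35%, alpha 0.05, power 80%, 10% loss). It reproduces with a two-sided normal approximation:

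n = [(1.960 × √(0.15 × 0.85) + 0.842 × √(0.35 × 0.65)) / 0.20]² = 30.32, rounded up to 31; 31 / 0.90 = 34.4, rounded up to 35.

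Here 35 serves only as the denominator, which assumes that every enrolled patient enters the safety set.

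**2. From the rule to the table.** Section 3.9 makes progression an SAE. Points D and E of the statistical method report the percentage of SAEs in the safety set. Section 3.10 names no exclusion. Nothing between the rule and the percentage takes progression out or tabulates it apart.

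**3. Step size.** A patient who already has another SAE adds nothing to a patient-level incidence. A patient whose only SAE is progression adds 1/35 = 2.86 points. Five such patients add 5/35 = 14.3 points.

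**4. Illustration.** The documents give no expected SAE or progression rate for this trial, so both counts below are assumptions. Intervals are Clopper-Pearson, n = 35.

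| Patients with a non-progression SAE | Progression-only patients | SAE incidence | 95% CI |
|---|---|---|---|
| 3 | 0 | 8.6% | 1.8 to 23.1 |
| 3 | 5 | 22.9% | 10.4 to 40.1 |
| 5 | 0 | 14.3% | 4.8 to 30.3 |
| 5 | 2 | 20.0% | 8.4 to 36.9 |
| 5 | 5 | 28.6% | 14.6 to 46.3 |
| 7 | 0 | 20.0% | 8.4 to 36.9 |
| 7 | 5 | 34.3% | 19.1 to 52.2 |

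Reporting progression on its own row returns each figure to the value in the row with zero progression-only patients.

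**5. Which progressions would count.** The recording rules differ:

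- Flow-chart description, note 4: SAEs up to 90 days after the last dose or until new anticancer therapy, whichever is first.
- Flow-chart description, note 10: once trial treatment has ended, only events related to it.
- Section 3.9, part 1: from enrolment to the end of the study. Part 4 agrees: "Any adverse events occurring during the study were monitored and followed up until the end of the study".
- Section 4.7, part 6: during treatment and for 30 days after the last cycle.

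Under note 10, a progression judged unrelated after treatment ends would not be recorded at all. Under section 3.9 it would. The number of progression SAEs therefore depends on which rule the site follows.

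**The case against.** **The endpoint is named as reactions, not events.** Section 3.9 defines a reaction by a reasonable possibility of a causal link, and its causality scale has an unrelated category that covers associated disease. A reader might infer that the safety endpoint as named is inflated. The documents do not support that: progression judged unrelated drops out of a serious adverse reaction rate. This stands and narrows the point to the all-cause SAE percentage, which is nevertheless what the statistical method says will be reported.

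**One event under two endpoints is not in itself an error.** Death is both an SAE and a DFS event, and an AE need not be caused by treatment, so an all-cause SAE rate was never a pure toxicity rate. That is fair. The difference is that death meets a seriousness criterion in its own right, whereas progression is admitted by rule, and section 3.10 says the safety analysis will hold no efficacy endpoints. That sentence stands under the interim-analysis heading, so its reach is open to argument.

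**Size.** A reader might infer that every recurrence over two years becomes an SAE, and apply the 29% to 39% distant metastasis rate cited in section 1.1. The documents do not support this. It takes the widest of several conflicting windows. The line says progression, while section 4.7 treats recurrence and metastasis after surgery separately. The cited rate is background, with no two-year horizon stated. Patients with another SAE would be counted as additional when they are not.

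**Treatment termination.** A reader might infer a direct clash between sections 4.6 and 3.5. The only required evaluation in 3.5 falls after consolidation and before surgery, and none of its PD paths continues the neoadjuvant drugs. The two can be read together, so what remains is a cross-reference to reconcile.

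**Benchmarks.** A reader might infer that a comparison with published SAE rates would be distorted. The plan specifies no such comparison, and section 1.2 cites adverse event rates of several kinds but no SAE rate.

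**Translation.** Two near-identical headings stand one after the other in section 3.9, and a *not* may have been lost from the second. The documents cannot settle this. If so, the current text says the opposite of what was meant and still needs correcting.

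**Conclusion.** Wrong as written. The plan tells sites to handle progression as an SAE, reports an all-cause SAE percentage, and provides no step that keeps the two apart. The conclusion rests on reading the section 3.9 line as it stands and on the analysis being of events, as the statistical method says.

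The firm part of the size is 2.9 points per progression-only patient with 35 in the safety set. The range of 0 to 14.3 points rests on an assumed 0 to 5 such patients and is not a forecast. The inflation could be nil if no progression falls inside the recording window or if every patient who progresses also has another SAE. The matter deserves correction because the effect falls on a reported secondary endpoint and the remedy is cheap.

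**What to change.** 1. Check the progression line in section 3.9 against the source-language text and state plainly whether progression counts as an SAE.
2. In the statistical method, state that the headline SAE incidence excludes progression and that progression appears on a separate row. This should hold whether or not progression is notified on the SAE form.
3. Use one term, event or reaction, in the endpoint lists and in the analysis text.
4. Choose one recording window for the endpoint and align flow-chart notes 4 and 10, section 3.9 and section 4.7 part 6 with it.
5. Reconcile the section 3.9 line with sections 3.5 and 4.6. Which clinical rule applies is for the investigators to decide.

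The cost is a few sentences and one table row. Sample size is unaffected, and progression is already recorded for the response assessment. The gain is a headline SAE rate that no longer contains progression.

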4.1 Sample size of the study

Sample size estimation (by single group)

Statistical test efficacy was calculated with postoperative pathologic complete response rate (pCR) as the primary study endpoint. α 0.05, the test efficacy is 80%, the postoperative pathological complete response rate after conventional treatment is 15%, and the estimated postoperative pathological complete response rate in the test group is 35%. Considering the loss of 10% of cases, the calculated sample size of the access group is 35 cases.

4.2 subject investigated

The study subjects of this project were obtained from 35 patients with pMMR / MSS locally advanced rectal cancer initially diagnosed in Yunnan Cancer Hospital (the Third Affiliated Hospital of Kunming Medical University) from September 2022 to March 2024.

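### The one-sample hypothesis that sized the trial (pCR 15% versus 35%) is not carried into the analysis plan, which instead names a non-inferiority analysis that a single-arm trial cannot run

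*Combined protocol and SAP*

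**What the plan says.** **Design.** Section 3 states: "This topic is a single-arm, single-center, prospective phase II clinical study". There is no control group.

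**Sizing.** Section 4.1, labelled as a single-group calculation, gives "α 0.05, the test efficacy is 80%, the postoperative pathological complete response rate after conventional treatment is 15" per cent, and "the estimated postoperative pathological complete response rate in the test group is 35" per cent. With 10% loss this leads to 35 patients. The synopsis repeats these figures. Neither place says whether the 5% is one- or two-sided.

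**Primary analysis.** The synopsis item on the primary-endpoint method says only that two pathologists assess pCR jointly after neoadjuvant treatment. It names no test, interval or threshold. The synopsis also describes most of the reported data as descriptive.

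**Section 3.10.** Counts are summarised as rates, and the 95% interval is attached to measurement data. The tests listed are "t-test for measurement data when comparing two groups, chi-square test for count data", followed by log-rank and Cox methods, with a general 0.05 bound tied to no endpoint. All enrolled patients and the per-protocol set are named for primary efficacy. The intention-to-treat set is then defined by randomisation to one of two arms, and the section adds: "Non-inferiority analysis will be performed in the per-protocol population". No margin or comparator is given.

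**The concern.** The 15% reference rate is the reason for enrolling 35 patients, yet it appears only in the sample-size paragraphs. The one efficacy comparison that section 3.10 ties to a named analysis set is non-inferiority. That needs a comparator and a margin, and the plan has neither. It is also the wrong kind of question, since section 1.2 gives the purpose of adding envafolimab as improving the pCR rate further.

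At stake is how the primary result is read. Without a stated test, sidedness and bar, a pCR count near the boundary can be called a success or a failure against the same 15%, and the choice could be made after the count is known. Correcting the population definitions alone would not help, because a sound analysis set would still have no comparison attached to it.

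**Working it through.** **Inputs.** p0 = 0.15, p1 = 0.35, alpha = 0.05, power 80%, 10% loss, N = 35 (section 4.1 and synopsis). Sidedness is not given, so both readings are shown.

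**1. Reproduce N.** One-sample normal approximation:

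n = [(z_alpha √(p0(1−p0)) + z_0.80 √(p1(1−p1))) / (p1 − p0)]²

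- Two-sided 5%: [(1.960 × 0.3571 + 0.8416 × 0.4770) / 0.20]² = 30.3, so 31. Then 31 / 0.9 = 34.4, so **35**, the plan's figure.
- One-sided 5%: 24.4, so 25, then 28 after loss. With a continuity correction it is 30, then 34.
- A two-arm comparison of 15% and 35% would need 73 per arm (two-sided) or 57 (one-sided).

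The 35 is therefore a one-sample calculation against 15%. The two-sided reading gives exactly 35, but this is an inference and not something the plan states.

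**2. Bars under an exact binomial test against 15%.** For each n, take the smallest r with P(X ≥ r | 0.15) at or below the level. Power is P(X ≥ r | 0.35). Results are given for all 35 patients and for the 31 evaluable patients from step 1.

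| Upper-tail level | n | Success at | Type I error | Power |
|---|---|---|---|---|
| 0.05 | 35 | ≥ 10 (28.6%) | 0.029 | 0.835 |
| 0.05 | 31 | ≥ 9 (29.0%) | 0.034 | 0.811 |
| 0.025 | 35 | ≥ 11 (31.4%) | 0.011 | 0.728 |
| 0.025 | 31 | ≥ 10 (32.3%) | 0.012 | 0.689 |

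The 0.025 rows are equivalent to asking that the lower exact (Clopper-Pearson) 95% limit exceed 15%. That limit is 16.9% at 11/35 and 16.7% at 10/31.

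**3. Where the choice decides the result.**

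- 10/35: exact one-sided p = 0.029, a success at one-sided 5%. The lower exact 95% limit is 14.6%, a failure at two-sided 5%.
- 9/31: exact one-sided p = 0.034, but the lower limit is 14.2%. The split is the same.
- A one-sample chi-square test differs again. At 10/35, z = (0.2857 − 0.15) / √(0.15 × 0.85 / 35) = 2.25, two-sided p = 0.025. At 9/31, z = (0.2903 − 0.15) / √(0.15 × 0.85 / 31) = 2.19, two-sided p = 0.029. Both succeed at two-sided 5%, where the exact interval fails.
- 9/35: exact one-sided p = 0.069, a failure at both exact bars.

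**4. Power under the stricter exact choice.** At upper-tail 0.025, 80% power is first reached with 34 evaluable patients (≥ 10/34, type I 0.024, power 0.805). That is 34 / 0.9 = 37.8, so 38 enrolled. Exact power moves in steps as n grows and stays above 80% only from 41 evaluable onwards.

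**The case against.** The best defence is that the hypothesis is already on paper. Section 4.1 fixes the endpoint, the 15% reference, the 35% target, alpha and power, and section 3.10 adds a 0.05 bound. The study is labelled exploratory and would report a pCR rate in named sets. The chi-square test for count data could be run as a one-sample test against 15%, which matches the calculation that gives 35. The two-group wording may refer to subgroups within the cohort.

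Much of this stands, and it rules out several stronger readings that a reader might infer:

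- *That the plan makes two-group tests its primary analysis.* Section 3.10 never calls them primary; they sit in a general methods paragraph.
- *That no listed test could address pCR against 15%.* A one-sample chi-square could. The plan does not say that this is meant.
- *That the plan yields no primary result.* It yields a descriptive rate.
- *That the comparator is open to later choice among the pCR rates quoted in section 1.2 (9.4% to 58.3%).* Section 4.1 fixes 15%, and a different reference would visibly contradict it. Of the quoted rates, only 9.4% comes from a control group without immunotherapy. The ambiguity shown above arises with 15% held fixed.
- *That the sample size is wrong.* It reproduces.

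What the defence does not meet is the absence of a stated test, sidedness, interval or bar for pCR, and the non-inferiority sentence, which a subgroup reading cannot rescue.

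**Conclusion.** The point holds. The plan sizes a one-sample comparison of pCR with 15% and then does not plan it. In its place stands a non-inferiority analysis without margin or comparator, which this design cannot run and which does not match the aim of improvement.

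The practical size is one response at the boundary. The exact bar is 10 or 11 of 35 (9 or 10 of 31) depending on a sidedness that the plan omits, and exact power is 0.835 or 0.728 at 35 (0.811 or 0.689 at 31). These figures assume an exact binomial test, the 15% and 35% of section 4.1, and denominators of 35 or 31. They show ambiguity from sidedness and choice of test, and nothing beyond that.

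**What to change.** 1. In section 3.10, delete the non-inferiority sentence.
2. In the synopsis item on the primary endpoint and in section 3.10, state that the primary analysis compares the pCR proportion with the fixed 15% of section 4.1 by a one-sample exact binomial test, reported with an exact 95% confidence interval.
3. Declare the sidedness in section 4.1 and in the analysis text, since there is none to copy, and state the bar and power that follow. At one-sided 5% this is ≥ 10/35 (power 0.835) or ≥ 9/31 (0.811), consistent with the stated 80%. At one-sided 2.5% (two-sided 5%) it is ≥ 11/35 (0.728) or ≥ 10/31 (0.689), and the 80% statement must be revised.
4. Label the t-test, chi-square and log-rank comparisons as exploratory comparisons within the cohort.

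The cost is wording, with no added procedures and no added patients if 35 is kept. The success bar is then fixed in advance. Under the two-sided exact choice, the plan must either admit power below 80% or enrol more patients to restore it.

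### The per-protocol and ITT definitions in section 3.10 cannot be applied as written in a single-arm trial, and no rule says how an enrolled patient without a surgical specimen counts for pCR

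*Combined protocol and SAP*

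**What the plan says.** Section 3 describes the design: "This topic is a single-arm, single-center, prospective phase II clinical study". The analysis sets are defined only in section 3.10, under the type of analysis.

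- **Primary analysis.** The primary efficacy analysis "will be performed in all enrolled populations (the intent-to-treat population or the ITT population) and the per-protocol population (PP". The two sets are not ranked.
- **ITT.** "The intention-to-treat population consists of all patients randomized to any of the two treatment arms".
- **Per-protocol.** The whole definition, apart from a sentence on analysis by randomized group, is: "Patients who have not received any dose of chemotherapy or chemoradiotherapy, or those who have suffered a serious violation of the inclusion or exclusion criteria".
- **Non-inferiority.** "Non-inferiority analysis will be performed in the per-protocol population". No comparator or margin is given.
- **Synopsis, statistical method.** It uses other labels: "For the PPS and FAS data, and safety indicators for the SS data". FAS is never defined. On the primary endpoint it says only that two pathologists evaluate pCR jointly; no denominator is given.
- **Sample size, section 4.1.** "Statistical test efficacy was calculated with postoperative pathologic complete response rate (pCR) as the primary study endpoint". The rates are 15% (conventional treatment) and 35% (test group), with alpha 0.05 and power 80%. "Considering the loss of 10% of cases, the calculated sample size of the access group is 35 cases".
- **Routes to no specimen.** Section 3.5 provides for observation after CR when anal preservation is impossible, an MDT decision for progression that cannot be resected R0, and guideline treatment for distant metastasis. Section 4.5 allows withdrawal. Section 3.4 offers watch-and-wait to patients with cCR without the anal-preservation condition.

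**The concern.** Read literally, one of the two sets carrying the primary analysis holds only untreated patients and serious eligibility violators, and the formal definition of the other set is empty. A statistician would have to reinterpret both before analysing anything.

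The wording can be repaired by common sense; the missing classification rule cannot. pCR is read on a resected specimen. The patients who may have none sit at both ends of response: clinical complete responders under observation, and patients with unresectable progression or metastasis. Dropping them, counting them as failures, or crediting the complete responders gives three different headline rates. Sections 3.4 and 3.5 also differ on who may go to watch-and-wait, so even the likely number of such patients is unsettled.

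**Working it through.** **Inputs.** From section 4.1: p0 = 0.15, p1 = 0.35, alpha 0.05 (sidedness not stated), power 80%, loss 10%, N = 35. Assumed, because the documents forecast neither: 4 patients without a specimen (range 0 to 6) and 9 observed pCRs.

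**1. The plan's own figure.** The one-sample normal approximation, two-sided 0.05, is

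n = [(1.960·√(0.15·0.85) + 0.842·√(0.35·0.65)) / 0.20]² = 30.3, so 31.

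31 / 0.90 = 34.4, so 35. The plan's N reproduces. An exact binomial test at one-sided 0.05 also supports 31: success at 9 or more, P(X≥9 | 31, 0.15) = 0.034, power P(X≥9 | 31, 0.35) = 0.811.

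**2. The estimate under three rules.** 9 pCRs; p is the exact one-sided tail against 15%.

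| No specimen | Count as non-pCR | Dropped | All cCR, counted as responders |
|---|---|---|---|
| 0 | 9/35 = 25.7%, p = 0.069 | same | same |
| 2 | 9/35 = 25.7%, p = 0.069 | 9/33 = 27.3%, p = 0.0495 | 11/35 = 31.4%, p = 0.011 |
| 4 | 9/35 = 25.7%, p = 0.069 | 9/31 = 29.0%, p = 0.034 | 13/35 = 37.1%, p = 0.001 |
| 6 | 9/35 = 25.7%, p = 0.069 | 9/29 = 31.0%, p = 0.022 | 15/35 = 42.9%, p = 0.0001 |

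The first two rules fall on opposite sides of 0.05 only near the threshold. With 11 pCRs and 4 without a specimen, 11/35 gives p = 0.011 and 11/31 gives p = 0.004.

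**3. Expected rate.** If 35% applies to operated patients and m patients count as non-pCR, the expected rate is 0.35·(35 − m)/35 = 0.35 − 0.01m, a loss of 1 percentage point per patient.

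**4. Power, exact one-sided 0.05.** The threshold with all 35 in the denominator is 10, since P(X≥10 | 35, 0.15) = 0.029. If 35% applies to operated patients:

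| No specimen | Operated only | All 35, no specimen = non-pCR |
|---|---|---|
| 0 | 83.5% (10/35) | 83.5% |
| 2 | 86.8% (9/33) | P(X≥10 given 33, 0.35) = 77.0% |
| 4 | 81.1% (9/31) | P(X≥10 given 31, 0.35) = 68.9% |
| 6 | 73.6% (9/29) | P(X≥10 given 29, 0.35) = 59.2% |

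If 35% is instead the rate among all 35 enrolled, power is P(X≥10 | 35, 0.35) = 83.5% however many lack a specimen.

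**5. Search for a correcting text.** Section 4.7 asks that complete pathological response be reported, but for postoperative specimens. Section 3.10 says no data are excluded, which does not classify an unoperated patient. Neither closes the gap.

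**The case against.** Much of the set wording can be read sensibly. The per-protocol entry stands under a heading about conforming to the protocol, so its list is almost certainly one of exclusions. ITT is usable from the phrase about all enrolled patients in the same section. The two-arm and non-inferiority text cannot be carried out, so it changes no result. The trial is exploratory and mostly descriptive, and it has no pCR success rule. All of this stands: on their own, these points would be clarifications.

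A reader might infer more than the documents support in four ways.

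- *That the denominator is wholly free to be chosen after the data are seen.* Section 3.10 names all enrolled patients for the primary analysis and says the sets are identified before database lock. What is open is the classification of patients without a specimen and the weight of ITT against PP.
- *That sections 3.10 and 4.1 set rival denominators.* A 10% loss allowance is routine inflation, and calling pCR postoperative describes when it is read. The figure of 31 is itself inferred; other standard methods give totals such as 28, 34 or 40 after loss.
- *That the trial is underpowered.* The fall in power needs 35% to apply to operated patients only, and several unoperated patients counted as non-pCR. With none missing, or with 35% applying to all enrolled, power is 83.5%. In the closest precedent cited in section 1.2, 28 of 32 had been operated and the other 4 were still on treatment; none is reported as finishing unoperated.
- *That a corrected PP set would inflate pCR.* The direction is not fixed, because a treated eligibility violator can reach pCR: removing one such patient moves 10/35 (p = 0.029) to 9/34 (p = 0.059).

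An operated-only rate is also a defensible comparison, since the background studies report pCR that way (16/28; 27 patients undergoing surgery). That supports reporting it, but not leaving the primary rule unstated.

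**Conclusion.** The point holds and should be fixed. The per-protocol, ITT and non-inferiority text is wrong as written and uncorrected elsewhere, and the primary endpoint lacks a rule for patients without a specimen.

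In the illustration (9 pCRs, 4 of 35 unoperated) the reported rate runs from 25.7% to 29.0% to 37.1% according to the rule; with no unoperated patients the three coincide. If 35% is the rate in operated patients, power is 81.1% operated-only against 68.9% when 4 count as non-pCR. These figures rest on assumed counts and an assumed one-sided exact test. With no success rule, the consequence is for the published estimate and the meaning of the 80% power, not for a formal decision.

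**What to change.** 1. Define ITT (or FAS) as all enrolled patients, without reference to randomization, and make it the primary set for pCR.
2. Define PP as ITT excluding patients with no study treatment or a serious eligibility violation, as a sensitivity analysis.
3. Delete the two-arm, assigned-group and non-inferiority text, and use one set of names in the synopsis and section 3.10.
4. State before database lock that patients without a specimen count as non-pCR in the primary analysis. Report pCR among operated patients, and watch-and-wait cCR, separately.
5. Reconcile sections 3.4 and 3.5 on who may enter watch-and-wait, since this drives the number without a specimen.
6. State that the 80% power refers to about 31 evaluable patients and is lower if unoperated patients count as non-pCR.

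**Cost.** The changes are to wording only, and N stays 35. The price is a slightly lower headline pCR rate, about 1 percentage point per patient without a specimen, and a less favourable stated power.
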